1. PREFACE

The Statistical Analysis Plan (SAP) for “A Multicenter, Adaptive, Randomized Blinded Controlled Trial of the Safety and Efficacy of Investigational Therapeutics for the Treatment of COVID-19 in Hospitalized Adults” (DMID Protocol 20-0006) describes and expands upon the statistical information presented in the protocol. This protocol is an adaptive protocol with different stages. Each stage will have a separate SAP. This SAP is for the study’s 2nd stage “ACTT-2”: Baricitinib + Remdesivir vs. Remdesivir.

This document describes all planned analyses and provides reasons and justifications for these analyses. It also includes sample tables, listings, and figures planned for the final analyses. Regarding the final analyses and Clinical Study Report (CSR), this SAP follows the International Conference on Harmonisation of Technical Requirements for Registration of Pharmaceuticals for Human Use (ICH) Guidelines, as indicated in Topic E3 (Structure and Content of Clinical Study Reports), and more generally is consistent with Topic E8 (General Considerations for Clinical Trials) and Topic E9 (Statistical Principles for Clinical Trials). The structure and content of the SAP provides sufficient detail to meet the requirements identified by the Food and Drug Administration (FDA) and ICH, while all work planned and reported for this SAP will follow internationally accepted guidelines published by the American Statistical Association and the Royal Statistical Society for statistical practice.

This document contains: a review of the study design, general statistical considerations, comprehensive statistical analysis methods for efficacy and safety outcomes, and a list of proposed tables, figures and listings. Within the table, figure, and listing mock-ups (Appendices 1, 2, and 3), references to CSR sections are included. Any deviation from this SAP will be described and justified in protocol amendments and/or in the CSR, as appropriate. The reader of this SAP is encouraged to also review the study protocol for details on conduct of the study and the operational aspects of clinical assessments.

2. INTRODUCTION

A preliminary review of data from ACTT-1 occurring after 606 recoveries and 103 deaths (approximately 67% of the 1063 subjects enrolled) demonstrated that subjects that received remdesivir had a 31% faster time to recovery (11 vs 15 days, recovery rate ratio 1.312 (1.119, 1.541), $p < 0.001$), and a decrease in mortality (8.0% vs 11.6%, $p = 0.059$). The Data and Safety Monitoring Board (DSMB) asked that the sponsor be unblinded early given public health implications and implications for ACTT-2. While an antiviral appears to have some efficacy in the treatment of COVID-19, the mortality rate is still high. Infection by pathogenic coronaviruses (e.g. SARS and SARS-CoV-2) often results in excessive cytokine and chemokine action with the development of acute respiratory distress syndrome (ARDS). It is postulated that this dysregulated inflammatory immune response is contributing to the excessive mortality and targeting this response will further improve outcomes.

Baricitinib, an orally administered, selective inhibitor of Janus Kinase (JAK)1 and JAK2, could be a therapeutic option because of the potential to inhibit signaling from multiple cytokines in COVID-19 patients. Baricitinib inhibits signaling of cytokines implicated in COVID-19, including interleukin (IL) IL-2, IL-6, IL-10, Interferon gamma (IFN- γ), and Granulocyte colony-stimulating factor (G-CSF), with lower IC₅₀ values translating to a greater overall inhibition of STAT signaling during the dosing interval. Baricitinib treatment resulted in a reduction from baseline in serum IL-6 at Week 12 in patients with active rheumatoid arthritis (RA) in a Phase 2, randomized, placebo-controlled study of baricitinib (data on file). The potent anti-inflammatory effects of baricitinib have also been demonstrated by the reduction of serum levels of IFN- γ , IP-10, Granulocyte-macrophage colony-stimulating factor (GM-CSF) and monocyte chemoattractant protein (MCP-1) in pediatric patients with steroid-dependent chronic inflammation, resulting in control of disease activity and the ability to wean or taper steroids.

Baricitinib is already approved for treatment of rheumatoid arthritis. It is administered orally once a day, with good oral bioavailability. It has a short half-life (approximately 12 hours in RA patients), so treatment can be interrupted or stopped if necessary. It has few drug-drug interactions (due to low CYP inhibitory activity) so it can be given concomitantly with background therapies. Baricitinib has a well-established safety profile, based on clinical trial data and post-marketing data in patients with RA. This profile, together with the observation that baricitinib is a potent AAK1/BIKE/GAK inhibitor with known anti-cytokine effects, provide the rationale to study baricitinib in the context of a randomized, controlled clinical trial in patients with COVID-19.

2.1. Purpose of the Analyses

This SAP encompasses all interim analyses and the final analysis of primary and secondary outcome measures. These analyses will assess the efficacy and safety of baricitinib + remdesivir in comparison with remdesivir and will be included in the Clinical Study Report. This protocol is an adaptive design and, if the design is modified, the SAP will be amended accordingly. The protocol for DMID 20-0006 calls for a planned interim efficacy analysis once roughly 33% of the targeted number of recoveries have been observed, and ongoing safety analyses. Safety interim analyses occur more frequently to review safety data in the event that the experimental agent inflicts harm. The goal of the efficacy interim analyses is to review endpoint data in order

to recommend whether the current study arm should proceed or to stop early for benefit or futility.

This SAP describes the planned analysis to be conducted by the Investigational New Drug (IND) sponsor NIAID. Additionally, there will be a separate analysis by the Manufacturer, Lilly USA, in which Lilly will:

- Define key secondary endpoints that will be tested with adjustments for multiple comparison. The adjustment is through a graphical testing scheme that controls for family-wise type I error;
- Pre-specify details of handling of intercurrent events including imputation procedures;
- Define additional analysis of time-to-event data that account for competing risk;
- Define additional safety analysis will also be pre-specified in the Addendum SAP

These analyses are useful to the manufacturer for regulatory purposes and will be pre-specified in an Addendum to this SAP.

3. STUDY OBJECTIVES AND ENDPOINTS

3.1. Study Objectives

Primary Objective

To evaluate the clinical efficacy, as assessed by time to recovery, of different investigational therapeutics as compared to the control arm.

Secondary Objectives

The key secondary objective is to evaluate the clinical efficacy of different investigational therapeutics relative to the control arm in adults hospitalized with COVID-19 according to clinical status (8-point ordinal clinical scale) at Day 15.

The other secondary objectives are to:

1. Evaluate clinical efficacy of different investigational therapeutics as compared to the control arm as assessed by:
 - Clinical Severity
 - 8-Point Clinical Status Ordinal scale:
 - Time to an improvement of one category and two categories from Day 1 (baseline) on the clinical status 8-point ordinal scale.
 - Subject clinical status using 8-point ordinal scale at Days 3, 5, 8, 11, 15, 22, and 29.
 - Mean change in the clinical status 8-point ordinal scale from Day 1 to Days 3, 5, 8, 11, 15, and 29.
 - National Early Warning Score (NEWS):
 - Time to discharge or to a NEWS of ≤ 2 and maintained for 24 hours, whichever occurs first.
 - Change from Day 1 to Days 3, 5, 8, 11, 15, and 29 in NEWS.
 - Oxygenation:
 - Oxygenation use up to Day 29.
 - Incidence and duration of new oxygen use through Day 29.
 - Non-invasive ventilation/high flow oxygen:
 - Non-invasive ventilation/high flow oxygen use up to Day 29.
 - Incidence and duration of new non-invasive ventilation or high flow oxygen use through Day 29.
 - Invasive Mechanical Ventilation / extracorporeal membrane oxygenation (ECMO):
 - Ventilator/ECMO use up to Day 29.
 - Incidence and duration of new mechanical ventilation or ECMO use through Day 29.

- Hospitalization
 - Duration of hospitalization (in days) through Day 29.
 - Mortality
 - 14-day mortality.
 - 28-day mortality.
2. Evaluate the safety of the intervention through 28 days of follow-up as compared to the control arm as assessed by:
- Cumulative incidence of SAEs through Day 29
 - Cumulative incidence of Grade 3 and 4 clinical and/or laboratory AEs through Day 29.
 - Discontinuation or temporary suspension of study product administrations (for any reason).
 - Changes in white cell count (WBC) with differential, hemoglobin, platelets, creatinine, glucose, total bilirubin, alanine aminotransferase (ALT), aspartate aminotransferase (AST), and prothrombin time (PT reported as INR), d-dimer, and C-reactive protein (CRP) over time (analysis of lab values in addition to AEs noted above).

Exploratory Objective

The exploratory objective is to evaluate the virologic efficacy of different investigational therapeutics as compared to the control arm as assessed by:

- Percentage of subjects with SARS-CoV-2 detectable in oropharyngeal (OP) sample at Day 3, 5, 8, 11, 15, and 29.
- Quantitative SARS-CoV-2 virus in OP sample at Day 3, 5, 8, 11, 15, and 29.
- Development of resistance of SARS-CoV-2 in OP sample at Day 3, 5, 8, 11, 15, and 29.
- Quantitative SARS-CoV-2 virus in blood at Day 3, 5, 8, and 11.

3.2. Endpoints

Primary Endpoint

Time to recovery, where recovery is defined as clinical status in states 1, 2, or 3 of the 8-point ordinal scale, censored at Day 29.

- Clinical status of a subject (8-point ordinal scale) is defined below:
 - 8. Death;
 - 7. Hospitalized, on invasive mechanical ventilation or ECMO;
 - 6. Hospitalized, on non-invasive ventilation or high flow oxygen devices;
 - 5. Hospitalized, requiring supplemental oxygen;
 - 4. Hospitalized, not requiring supplemental oxygen - requiring ongoing medical care (COVID-19 related or otherwise);

3. Hospitalized, not requiring supplemental oxygen - no longer requiring ongoing medical care;
2. Not hospitalized, limitation on activities and/or requiring home oxygen;
1. Not hospitalized, no limitations on activities

Secondary Endpoints

The key secondary endpoint is clinical status (8-point ordinal scale) on Day 15.

The other secondary endpoints are:

- Ordinal outcome assessed daily while hospitalized and on Days 15, 22, and 29.
- NEWS assessed daily while hospitalized and on Days 15 and 29.
- Days of supplemental oxygen (if applicable).
- Days of non-invasive ventilation/high-flow oxygen (if applicable).
- Days of invasive mechanical ventilation/ECMO (if applicable).
- Days of hospitalization.
- Date and cause of death (if applicable).
- SAEs.
- Grade 3 and 4 adverse events
- WBC with differentials, hemoglobin, platelets, creatinine, glucose, total bilirubin, ALT, AST, INR, d-dimer, and CRP on Day 1; Days 3, 5, 8, and 11 (while hospitalized); and Days 15 and 29 (if attends in-person visit or still hospitalized).

Exploratory Endpoint

- Qualitative and quantitative polymerase chain reaction PCR for SARS-CoV-2 in OP swab on Day 1; Days 3, 5, 8, and 11 (while hospitalized); and Days 15 and 29 (if attends in-person visit or still hospitalized).
- Qualitative and quantitative PCR for SARS-CoV-2 in blood on Day 1; Days 3, 5, 8, and 11 (while hospitalized).

3.3. Study Definitions and Derived Variables

3.3.1. Baseline Value

For efficacy assessments, the baseline value will be defined as the last value obtained prior to randomization. For safety assessments, the baseline value will be defined as the last value obtained prior to the first dose of study product on trial.

3.3.2. Recovery and Time to Recovery

The primary efficacy outcome measure is the time to recovery. Recovery will be defined as having a value of 1, 2, or 3 on the clinical status 8-point ordinal scale. The time to recovery will be defined as the elapsed time (in days) from randomization to the earliest day at which a subject

reaches recovery. Note that since clinical status assessments are recorded as defined in Section 4.3, the day that is being assessed (not necessarily the day the response is collected) will be used to determine the timing of events. For example, a subject with a score of 5 recorded on Days 1 - 3 and a score of 3 recorded on Day 4 will have a time to recovery equal to 3 days. It is also possible that a subject has a clinical status score > 3 reported for a particular day but was subsequently discharged on the same day. Such cases will be reviewed by the NIAID Medical Officer to make the determination of whether the subject should be considered recovered in analyses. Subject data to be reviewed as part of this determination will include the reported clinical status scores while hospitalized, where the subject was discharged to (e.g. private residence, rehabilitation facility, long-term care/nursing home), and any information regarding readmittance.

Any subjects that are lost to follow-up or terminated early prior to an observed recovery will be censored at the day of their last observed assessment. Subjects who complete follow-up but do not experience recovery will be censored at the day of their Day 29 visit. All deaths within Day 29 (and prior to recovery) will be considered censored at 28 days. Note that we do not expect many subjects to worsen after discharge.

However, we will evaluate whether any discharged subjects subsequently experience a worse clinical status and sensitivity analyses will be conducted accordingly. For these analyses, subjects who recover but are later re-admitted for COVID-19 will not be considered a recovery but will instead be censored at 28 days.

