3. OBJECTIVES AND ENDPOINTS

The overall objective of the study is to evaluate the clinical efficacy and safety of different investigational therapeutics relative to the control arm among hospitalized adults who have COVID-19.

OBJECTIVES	ENDPOINTS (OUTCOME MEASURES)
Primary	
To evaluate the clinical efficacy, as assessed by time to recovery, of different investigational therapeutics as compared to the control arm.	Day of recovery is defined as the first day on which the subject satisfies one of the following three categories from the ordinal scale: 
 • Hospitalized, not requiring supplemental oxygen – no longer requires ongoing medical care; • Not hospitalized, limitation on activities and/or requiring home oxygen; • Not hospitalized, no limitations on activities. Recovery is evaluated up until Day 29.
Key Secondary	
To evaluate the clinical efficacy of different investigational therapeutics relative to the control arm in adults hospitalized with COVID-19 according to clinical status (8-point ordinal scale) at Day 15	
 • Death; • Hospitalized, on invasive mechanical ventilation or ECMO; • Hospitalized, on non-invasive ventilation or high flow oxygen devices; • Hospitalized, requiring supplemental oxygen;

OBJECTIVES	ENDPOINTS (OUTCOME MEASURES)
	
 • Hospitalized, not requiring supplemental oxygen – requiring ongoing medical care (COVID-19 related or otherwise); • Hospitalized, not requiring supplemental oxygen – no longer requires ongoing medical care; • Not hospitalized, limitation on activities and/or requiring home oxygen; • Not hospitalized, no limitations on activities.
Additional Secondary	

To evaluate the clinical efficacy of different investigational therapeutics as compared to the control arm as assessed by:
 
 • Clinical Severity 
 ○ Ordinal scale: 
 ▪ Time to an improvement of one category and two categories from Day 1 (baseline) using an ordinal scale. ▪ Subject clinical status using ordinal scale at Days 3, 5, 8, 11, 15, 22, and 29. ▪ Mean change in the ordinal scale from Day 1 to Days 3, 5, 8, 11, 15, 22, and 29. 	
 • Clinical outcome assessed using ordinal scale daily while hospitalized and on Days 15, 22, and 29.

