3.3.10. Time to Death

For analysis of time to death, the time to death will be defined as the elapsed time (in days) from randomization (or treatment administration for the safety analysis) to death. Any subjects that are lost to follow-up or terminated early prior to death will be censored at the day of their last observed assessment or last captured event (e.g. the end date of an adverse event). If it is learned that a subject who terminated early had subsequently died prior to Day 29, then the subject will be classified as dead. Subjects who complete follow-up will be censored at the earliest of their Day 29 visit and (actual) Day 29. Deaths that occur after Day 29 will be censored at Day 29.

Similar censoring methods will be used for the 14-day mortality analyses in that deaths that occur after Day 15 will be censored at Day 15 and subjects who are confirmed alive through Day 15 will be censored at Day 15. Subjects whose last observed assessment or last capture event (e.g. the end date of an adverse event) is prior to Day 15 will be censored at that last observed assessment/event.

3.3.11. Composite Endpoint of Death, SAEs, Severe AEs, Discontinuation of Study Product Administrations

A safety composite endpoint will be defined as the occurrence of at least one of the following through Day 29:

1. Death

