6.5. Missing Data

All attempts will be made to collect all data per protocol. Any data point that appears to be erroneous or inexplicable based on clinical judgment will be investigated as a possible outlier. If data points are identified as outliers, sensitivity analyses may be performed to examine the impact of including or excluding the outliers. Any substantive differences in these analyses will be reported.

For time to event outcomes, subjects who are lost to follow-up or terminate the study prior to Day 29 and prior to observing/experiencing the event will be censored at the time of their last observed assessment. Subjects who die prior to observing/experiencing the event will be censored at Day 29.

For the analysis of the key secondary outcome, subjects who are discharged but are subsequently re-admitted prior to Day 15 without a reported clinical score, their clinical score will be imputed at 7, which is the highest value for a hospitalized subject.

For the analyses of the secondary outcomes that involve clinical score (i.e. the key secondary outcome and time to improvement), if a subject is discharged from the hospital without a previously or concurrently reported clinical score of 1 or 2, then their clinical score at the time of discharge will be imputed as 2, which is the highest value for a non-hospitalized subject. If a subject terminates early from the study while they are hospitalized or completes the study while still hospitalized, the last observed clinical score assessment will be used as their final assessment.

For the modified version of the ordinal score described in Section 4.3, if a subject is discharged from the hospital without a previously or concurrently reported clinical score of 2 or 3, then their clinical score at the time of discharge will be imputed as 3, which is the highest value for a non-hospitalized subject.

For the analyses of the secondary outcomes described in Section 3.3, the following imputation rules will be used for subjects who are lost to follow-up, terminate early from the study, or do not have further outcome data available after discharge for any reason:

- Days of Non-invasive ventilation/high-flow oxygen:

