8. EFFICACY EVALUATION

8.1. Primary Efficacy Analysis

8.1.1. Primary Analyses

The primary analysis uses the stratified log rank test to compare treatment to control through Day 29 with respect to time to recovery, as defined in Section 3.3. Stratification is based on moderate versus severe disease at baseline. As noted in Section 3.3, all deaths within 29 days will be considered censored at Day 29 with respect to time to recovery. Conceptually, a death corresponds to an infinite time to recovery, but censoring at any time greater than or equal to Day 29 gives the same answer as censoring at Day 29; both correspond to giving deaths the worst rank.

Let MM and S denote the Moderate and Severe subgroups, respectively. The z-score associated with the stratified log rank test is

$$Z = \frac{\sum_{MM}(O_i - E_i) + \sum_S(O_i - E_i)}{\sqrt{\sum_{MM} V_i + \sum_S V_i}}$$

The sums are over recovery times t_i in the moderate and severe subgroups, O_i is the number of treatment arm participants recovering at time t_i , and E_i and V_i are the null expected value and variance of the number of treatment recoveries calculated using the hypergeometric distribution. Specifically, if n_{Ti} and n_{Ci} denote the numbers of patients 'at risk' in the two arms in a given stratum at t_i , and r_i is the total number of recoveries at t_i , then $E_i = r_i n_{Ti} / (n_{Ti} + n_{Ci})$ and $V_i = r_i (n_i - r_i) n_{Ti} n_{Ci} / [n_i^2 (n_i - 1)]$, where $n_i = n_{Ti} + n_{Ci}$. The O_i , E_i , and V_i are computed separately within the moderate and severe strata.

As noted in Section 6.6.2, to maintain an overall two-sided type-I error rate of 0.05, the Lan-DeMets spending function analog of the O'Brien-Fleming boundary will be used to derive the cumulative error spending and boundaries for the interim analysis.

For the final analysis, the log rank test will be performed using the pseudocode provided in Section 6.1. The following pseudocode can be used to compute the bounds for the final analyses and compare to the calculated log-rank statistic. The Boundaries dataset will contain the updated boundaries calculated from the interim analyses using the actual information levels observed at the interim analysis.

```

data Params_LogR;
  set logrankp(rename=(Statistic=Estimate));
  if Variable='TreatmentVariable';
  _Scale_='Score';
  _Stage_= AnalysisNumber;
  keep Variable _Scale_ _Stage_ StdErr Estimate;
run;

proc seqtest Boundary=Boundaries

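### SAP 3.3.2 and 3.3.4 censor at a Day 29 visit that may fall on Days 26 to 32, without the cap at actual Day 29 that the endpoint definition implies and SAP 3.3.10 already uses

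*SAP*

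**What the plan says.** The schedule of assessments in Protocol Appendix B 1.2 gives the Day 29 visit a window of plus or minus 3 days, so it can take place on Days 26 to 32.

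SAP 3.3.2 derives time to recovery: "Subjects who complete follow-up but do not experience recovery will be censored at the day of their Day 29 visit". SAP 3.3.4 uses the same rule for time to improvement, and SAP 3.3.11 censors the safety composite at the Day 29 visit. None of the three mentions actual Day 29 as a limit on censoring.

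The endpoint is bounded elsewhere:
- Protocol Appendix B, section 3: "Recovery is evaluated up until Day 29".
- SAP 3.2 defines recovery as states 1 to 3 "of the 8-point ordinal scale, censored at Day 29".
- SAP 8.1.1: "The primary analysis uses the stratified log rank test to compare treatment to control through Day 29 with respect to time to recovery".

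For time to death, SAP 3.3.10 does state a cap: "Subjects who complete follow-up will be censored at the earliest of their Day 29 visit and (actual) Day 29".

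Deaths before recovery are placed in two ways. SAP 3.3.2: "All deaths within Day 29 (and prior to recovery) will be considered censored at 28 days". SAP 6.5: "Subjects who die prior to observing/experiencing the event will be censored at Day 29". SAP 8.1.1 also uses Day 29, and argues that the exact day is immaterial because "censoring at any time greater than or equal to Day 29 gives the same answer as censoring at Day 29".

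**The concern.** The derivation rule and the endpoint definition disagree on when follow-up for the primary endpoint ends. A programmer working from 3.3.2 would let follow-up run to the visit date, and the log-rank and Cox pseudocode in SAP 6.1 contains no truncation. A recovery recorded at a late visit could then enter the primary test.

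Two things follow from that reading. Whether a late recovery counts would depend on when the site scheduled the last contact. It would also be compared against a risk set that deaths had already left, so deaths would no longer hold the worst rank. The 8.1.1 argument is sound only if no event is counted after the time at which deaths are censored.

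The window works in the other direction too. A completer seen on Days 26 to 28 is censored before the deaths are, and any recovery between that visit and Day 29 may be missed.

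**Working it through.** **1. The plan's own sizing.** SAP 5 asks for 723 recoveries for a recovery rate ratio of 1.25, two-sided alpha 0.05 and 85% power. With z_beta rounded to 1.04, 4(1.96 + 1.04)² / (ln 1.25)² = 36 / 0.04979 = 723. At 70% recovery, 723 / 0.70 = 1032.9, stated as 1032. Both reproduce, and neither depends on the censoring rule.

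**2. The time scale.** Under SAP 4.3 a score recorded on Day d describes Day d − 1. In the worked example in 3.3.2, a score recorded on Day 4 gives a time of 3 days. On that scale a score recorded on Day 29 has time 28, and scores recorded on Days 30, 31 and 32 have times 29, 30 and 31. Deaths censored at 28 days have left the risk set at all three. The exposed days are therefore about Days 29 to 31 as assessed. A recovery assessed on Day 29 itself has time 29 and follows deaths placed at 28 days, so the choice between 28 days and Day 29 matters in its own right.

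**3. Can such scores exist?** Appendix B 8.1.2.2 ends daily inpatient scoring at Day 29. Footnote 8 of the schedule of assessments lets daily collection run to discharge or end of study, and a visit on Days 30 to 32 itself records an ordinal score. So they can.

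**4. How many events?** The documents do not give ACTT-2 mortality, the late recovery hazard or the spread of visit days. Assumptions: mortality m of 5 to 15% (ACTT-1 reported 8.0% and 11.6%) and a daily recovery probability h of 0.01 to 0.06 after Day 29.

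- Alive and unrecovered: 1032 × (1 − 0.70 − m), which is 258, 206 and 155 for m = 5%, 10% and 15%.
- Visits spread evenly over seven days: multiply by [h + 1 − (1 − h)² + 1 − (1 − h)³] / 7.
- Every visit on Day 32 (upper bound): multiply by 1 − (1 − h)³.

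| m | h | even spread | all on Day 32 |
|---|---|---|---|
| 15% | 0.01 | 155 × 0.0085 = 1.3 | 155 × 0.0297 = 4.6 |
| 10% | 0.02 | 3.5 | 12.1 |
| 5% | 0.06 | 258 × 0.0494 = 12.7 | 258 × 0.1694 = 43.7 |

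Against 723, an even spread gives 0.2 to 1.8% and the upper bound 0.6 to 6.0%. If late visits are uncommon the count is close to nil. With 15% of 1032 alive and unrecovered, 10% of them seen late, 2 extra days and h = 0.01, it is 1032 × 0.15 × 0.10 × (1 − 0.99²) = 0.3.

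**5. Effect on the test.** The two rules (cap at Day 29, or visit day) were compared by simulation: 516 per arm, unstratified log-rank, 1500 replicates per scenario, late hazard 0.02 or 0.043 per day. The latter is −ln(0.30)/28, the constant hazard that gives 70% recovery in 28 days.

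- True ratio 1.25: power 0.844 to 0.855 with the cap and 0.838 to 0.868 with the visit-day rule; largest difference within a scenario 1.3 points.
- Mean hazard ratio: moved by less than 0.004.
- Null: rejection 0.045 to 0.059 with the cap and 0.043 to 0.060 with the visit-day rule, including 12% versus 6% mortality. The Monte Carlo standard error is √(0.05 × 0.95 / 1500) = 0.006.
- Where visits did not all fall on Day 29, the rules gave different significance calls in about 1 to 3% of replicates.

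**6. Net direction.** With visits spread evenly, the visit-day rule gave fewer events in total, about 714 to 719 against 722 to 723. Recoveries cut off by early visits outnumbered those gained from late ones.

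**The case against.** The best defence is that the horizon is already settled. SAP 3.2, SAP 8.1.1 and the protocol all stop at Day 29, Table 24 reports recoveries by Day 29, and the sentence in 3.3.2 only places the censoring mark for people who did not recover. If events stop at Day 29, moving that mark from Day 29 to Day 32 leaves the log-rank statistic unchanged and the 8.1.1 argument holds. This reading is plausible and may be what the authors intend. But 3.3.2 does not say it, the pseudocode does not enforce it, and 3.3.10 shows that the SAP states a cap where it means one. It also does nothing for visits on Days 26 to 28.

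A second point stands in part. Patients still unrecovered are mostly inpatients, scored daily through Day 29, whereas late contacts mainly concern discharged patients who have usually recovered already. An even spread of visit days may therefore overstate the exposure. In addition, a patient discharged late may score above 3 for that day, and 3.3.2 sends such cases to medical review.

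A third point stands. SAP 3.3.11 defines the composite as occurring through Day 29, so its events are already bounded and only its censoring wording needs alignment.

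A reader might infer that the plan does count recoveries on Days 30 to 32 as primary events. The documents do not support that: no passage says so, several contradict it, and the exposed days as assessed are about 29 to 31.

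**Conclusion.** The inconsistency is real and minor. SAP 3.3.2 and 3.3.4 lack the cap that the endpoint definition implies and that 3.3.10 uses for death, and the 8.1.1 statement about deaths is secure only once that cap and a single time scale are in place.

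On the assumed mortality, late hazard and visit spread, roughly 0 to 13 of 723 events are affected if visits spread evenly. The figure of about 44 needs every visit to fall on Day 32 together with the most favourable late hazard, and is only a bound. Power, hazard ratio and type I error do not change meaningfully, and 723 events and N = 1032 stand. The reason to act is that a primary endpoint should not have two readings that can occasionally disagree on significance.

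A reader might also infer a bias towards one arm. Nothing in the documents or the calculations shows one: the rule applies equally to both arms, the oral product is blinded, and unequal mortality did not disturb the null rejection rate. It would take visit timing that differed by arm.

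**What to change.** In SAP 3.3.2 and 3.3.4, state that events after actual Day 29 are not counted and that completers without the event are censored no later than actual Day 29. Where the visit was early, use daily inpatient scores through Day 29 if they exist; adopting the 3.3.10 wording alone would still censor those patients at the early visit. Put the same limit in 3.3.11 so that its censoring matches its own definition.

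Choose one time scale for Day 29 and for censoring deaths, either 28 days or Day 29, and use it in 3.3.2, 6.5 and 8.1.1. Make clear on that scale how a recovery assessed on Day 29 itself is timed relative to deaths.

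The cost is a clause per section. No new data are needed and the sizing is unchanged. The downside is that a handful of late events may be dropped.
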